#### 6.4.3 Known Potential Benefits

In patients with AF, elimination of or a reduction in symptoms is a major driving force for therapy. The primary clinical benefit of ablation of AF is an improvement in QoL resulting from the elimination of arrhythmia-related symptoms such as palpitations, fatigue, or effort intolerance. The Circular IRE Catheter is intended to allow for the ablation of larger areas of tissue compared to traditional single tip catheters. Thus, the Circular IRE Catheter should possess the benefit of reduced procedure time and fewer catheter exchanges.

Influence on adjacent structures has been previously studied. Of the well described complications in RF ablation techniques, the tissue specificity of IRE has been considered as a major advantage.

Additionally, other PFA cardiac technologies, have shown in early reports that IRE creates durable lesions at effectiveness rates higher than that seen in radiofrequency trials.

Further reference can be made to the Risk-Benefit Analysis (RBA) for more information.

## 7. Objectives and Purpose

### 7.1 Objective

The primary objective of this clinical investigation is to demonstrate safety and long-term effectiveness of the IRE system (Circular IRE Catheter and IRE Generator) when used for isolation of the atrial PVs in treatment of subjects with PAF. Specifically:

[figure not shown]
- To demonstrate safety based on early-onset Primary Adverse Events (PAEs) (within 7 days following the ablation procedure).
- To demonstrate long term effectiveness based on the freedom from documented (symptomatic and asymptomatic) atrial arrhythmia (AF, Atrial Tachycardia (AT) or Atrial Flutter (AFL)) episodes based on electrocardiographic data ( $\geq 30$  seconds on arrhythmia monitoring device) during the effectiveness evaluation period (Day 91-Day 365).

### 7.2 Purpose

The primary purpose of this study is to prove that the use of the IRE Ablation System, incorporating both the Circular IRE Catheter and the IRE Generator, for the isolation of the PVs in treatment of subjects with PAF is safe and effective. The results of this provide evidence to support CE-mark registration of these devices

Wave I will serve as characterization of safety and provide preliminary estimates for safety and acute effectiveness of the system under study.

## 8. Study Design and Endpoints

\* Acute data from Wave I will be used for both, preliminary acute safety and acute performance, of the IRE system before proceeding with Wave II.

### 8.1 Description of the Study Design

The design of the study will be carried out as an interventional, prospective, multicenter, single-arm clinical study. The study will enroll subjects with drug refractory, symptomatic PAF who are candidates for catheter ablation. All study subjects will be followed though 12 months post-ablation.

For the purpose of characterization of safety and to provide preliminary estimates for safety and acute effectiveness of the IRE system, Wave I of the study will enroll up to 40 subjects, who will undergo the index procedure and additional neurological, PV and esophageal assessments. For the purpose of safety and long-term effectiveness Wave II of the study will enroll up to 330 main study phase subjects plus roll-ins. Acute data from Wave I will be assessed for both, preliminary acute safety and acute performance, of the IRE system before proceeding with Wave II. Wave II enrollment can be initiated when all Wave I subjects have

reached 7 days follow up unless the Sponsor deems otherwise per sections 25 (Study Suspension or Termination) and 6.4.2 (Minimization of Risk).

An adaptive Bayesian design to will be used to determine the sample size. Two sample size selection interim analyses will be performed based on the primary effectiveness endpoint. Study success as defined by the main study endpoints will be analyzed for the respective Wave II analysis populations further described in the statistical section of this protocol (section 20). An additional interim analysis will be performed for claiming early trial success when 30 subjects reach full 12-month of follow-up and all subjects reach three months of follow-up.

In Wave II, the first 1-3 subjects for each ablating physician will be considered roll-in subjects to verify consistent workflow for study device components and to minimize any learning curve effects. Operators whom performed procedures in Wave I may be exempted from roll-ins for Wave II per training charter. The roll-in phase will include a maximum of 180 subjects.

Subjects will be evaluated prior to the procedure, prior to discharge, and post procedure at 7 days (Day 7-9), 1 month (Day 23-37), 3 months (Day 76-104), 6 months (Day 166-194), and 12 months (Day 335-379).

### **8.1.1 Wave I Subjects**

A prospective evaluation of 40 subjects will be included in Wave I of the study. Wave I subjects will, in addition to the general study follow-up schedule, undergo additional neurological, PV and esophageal assessments. The subjects of Wave I will meet all inclusion and exclusion criteria, including the additional exclusion criteria specific to Wave I.

Additional assessments for Wave I subjects include:

1. Cerebral MRI, National Institute of Health Stroke Scale (NIHSS), Modified Rankin Scale (mRS), Mini Mental State Examination (MMSE) and general neurological assessments for evaluation of neurological incidences. Note: Patient questionnaires will only be used in countries with validated languages
2. Cardiac Computed Tomography (CT) or Magnetic Resonance Angiogram (MRA) at 3 months AND in case of symptoms, for evaluation of PV stenosis.
3. Endoscopy post-procedure for evaluation of esophageal lesions.

### **8.1.2 Wave II: Roll-In Subjects**

New devices often require operators to scale a learning curve. The inclusion of a roll-in phase in the study will allow learning for the operators, and an evaluation of safety and effectiveness of the device that is not diminished by the early learning curve. In addition to a requirement for IRE ablation System training for ablating physicians, further experience within the context of this clinical investigational plan will serve to generate a clearer perspective of the effectiveness of the IRE ablation System in treating PAF subjects. Therefore, as of Wave II, up to the first 3 subjects (operator dependent based on criteria defined per training charter) treated by an ablating physician with the study catheter will be prospectively assigned as roll-in subjects to minimize the learning curve effect. To allow for a wide range of physician skill level, up to three physicians per site will be able to participate. Because roll-in subjects are at the physician level, some physicians at a site may complete their roll-in subjects and move to the main study phase while other physicians at the site are still in the roll-in phase. A subject who is excluded or discontinued will not count toward the

roll-in subjects. Roll-in subjects will be followed for 12 months post index procedure. The results from the roll-in phase will be analyzed and presented separately from the main study phase.

### 8.1.3 Wave II: Main Study Phase Subjects

Eligible subjects who sign the Informed Consent Form (ICF) and who meet all eligibility will be enrolled and treated with the Circular IRE Catheter in conjunction with the IRE Generator. A maximum sample size of 330 subjects is planned the main phase. All main phase subjects will follow the same follow-up schedule as the other subjects namely be followed-up for 12 months after study procedure.

Planned statistical analyses of the endpoints and analysis populations are described in the Statistical Analysis section (section 20) of this clinical investigational plan and in the Statistical Analysis Plan (SAP).

## 8.2 Study Endpoints

Only Wave II subject data will be used for the purpose of primary hypothesis testing. Wave I and roll-in subject data will be separately analyzed (not part of the primary hypothesis testing), further described in the statistical section of this protocol (section 20).

### 8.2.1 Primary Endpoints

- **Acute Safety**

The primary safety endpoint is the incidence of PAEs (within seven (7) days of the initial mapping and ablation procedure). PAEs include the following AEs:

Atrio-Esophageal Fistula*	Phrenic Nerve Paralysis (permanent)
Cardiac Tamponade/perforation	Pulmonary Vein Stenosis*
Device or procedure related death*	Stroke/CVA
Major Vascular Access Complication/Bleeding	Thromboembolism
Myocardial Infarction	Transient Ischemic Attack (TIA)
Pericarditis	

\* Device or procedure related death, pulmonary vein stenosis and atrio-esophageal fistula that occur greater than one week (7 days) post-procedure are considered and analyzed as PAEs.

A 14% performance goal is set for the primary safety endpoint

- **Long term effectiveness:**

Freedom from documented (symptomatic and asymptomatic) atrial arrhythmia (AF, AT or AFL) episodes based on electrocardiographic data ( $\geq 30$  seconds on arrhythmia monitoring device) during the effectiveness evaluation period (Day 91-Day 365). Acute procedural failure (i.e., failure to confirm entrance block, with or without touch-up, in all PVs except those that are silent and/or cannot be cannulated post-procedure) will be considered a long-term effectiveness failure.

A 50% performance goal is set for the primary long-term effectiveness endpoint

Further refer to appendix 1 for definitions on long term effectiveness terms.

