### 8.2.2 Secondary Endpoints

- Acute Procedural Success defined as confirmation of entrance block in all clinically relevant targeted PVs after adenosine/isoproterenol challenge. Use of a non-study catheter to achieve PVI is considered an acute procedural success failure.
- Freedom from documented symptomatic atrial arrhythmia (AF, AT or AFL) episodes based on electrocardiographic data ( $\geq 30$  seconds on arrhythmia monitoring device) during the effectiveness evaluation period (Day 91-Day 365).
- Quality of Life: the change of QoL assessed by comparing the Atrial Fibrillation Effect on Quality-of-Life (AFEQT™) scores before and after the ablation procedure. Note: Patient questionnaires will only be used in countries with validated languages.

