### 8.2.3 Additional Endpoints

- **Safety**
  - Occurrence of individual PAEs from the primary composite
  - Occurrence of Serious Adverse Device Effects (SADEs)
  - Occurrence of Serious Adverse Events (SAEs) within 7 days (early-onset), 8-30 days (peri-procedural) and  $>30$  days (late onset) of initial ablation procedure
  - Occurrence of non-SAEs
  - Occurrence of clinically symptomatic severe PV stenosis as documented by CT/MRA
- **Effectiveness**
  - Ablation by a non-study catheter for PVI (touch-up) among all clinically relevant targeted PVs and by subject
  - Acute reconnection identified by adenosine/isoproterenol challenge.
  - % repeat ablation within the 12M FU period
    - Timing (blanking period or after blanking)
    - % PV reconnection
  - Freedom from documented (symptomatic and asymptomatic) atrial fibrillation (AF) episodes based on electrocardiographic data ( $>30$  seconds on arrhythmia monitoring device) during the effectiveness evaluation period (Day 91-Day 365).
  - Freedom from documented (symptomatic and asymptomatic) atrial arrhythmia (AF, AT or AFL) episodes based on electrocardiographic data ( $\geq 30$  seconds on arrhythmia monitoring device) during the effectiveness evaluation period (Day 91-Day 365) with the following criteria also deemed failure (Appendix 1):
    - Taking a new class I/III AAD for AF or a previously failed class I/III AAD at a greater than the highest ineffective historical dose for AF during the effectiveness evaluation period
    - Greater than 2 repeat ablations for AF/AT/AFL in the blanking period or any repeat ablation for AF/AT/AFL during the effectiveness evaluation period
- **Procedural data, including but not limited to**
  - Total procedure time
  - Mapping time

- PFA application time
  - Number of PFA applications by PV and by subject
  - Total fluoroscopy time
  - Study catheter dwell time
  - Ablation settings used
  - Use of paralytics and anesthesia
- **Neurological Assessment (Wave I)**
    - Occurrence of new post-ablation asymptomatic and symptomatic cerebral emboli as determined by MRI evaluations
    - Occurrence of new or worsening neurological deficits post-ablation and at follow-up, compared to baseline
    - Occurrence, anatomical location and size of asymptomatic and symptomatic cerebral emboli observed pre-and post-ablation as determined by MRI evaluations.

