### 20.3.2 Wave II Analysis Sets

- **Modified Intent-To-Treat (mITT-Wave II) Analysis Set:** The mITT-Wave II analysis set will consist of enrolled Wave II main study phase subjects who meet eligibility criteria and have had insertion of the study catheter—Subjects in this analysis set who are discontinued due to:
  - study catheter related reasons will be considered acute effectiveness failures
  - non-study catheter related reasons (other equipment, pump, anatomy that precludes treatment with the study catheter or commercially available catheter) will be excluded from the effectiveness analysis.
- **Full Analysis set (FAS-Wave II):** The FAS-Wave II Analysis Set will consist of all enrolled Wave II main study phase subjects who have had insertion of the study catheter (with or without delivery of PFA).
- **Per Protocol (PP-Wave II) Analysis Set:** The PP-Wave II analysis set will consist of Wave II main study phase subjects who satisfy the following criteria:
  - are enrolled and without major protocol deviations that would affect the integrity of the data
  - have undergone ablation (PFA) with the study catheter
  - are treated for the study-related arrhythmia
  - did not require the use of a non-study catheter for Pulmonary Vein Isolation (PVI)
  - did not require ablations outside the PV region
- **Roll-In Analysis Set:** The Roll-In analysis set will include all subjects who are enrolled in the roll-in phase. All endpoints will be analyzed for the roll-in analysis set separately.

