#### 20.4.4 Primary Endpoint Analyses and Associated Hypotheses

The primary safety endpoint will be summarized descriptively in the mITT-Wave I analysis set after all Wave I subjects complete the 12-month follow-up. Similarly, the primary effectiveness endpoint will be summarized descriptively in the PP-Wave I analysis set after all Wave I subjects complete the 12-month follow-up.

For the main study phase, the PAE rate will be formally compared against a performance goal of 14%. Additionally, the primary effectiveness success rate will be compared to a performance goal of 50% for the main study phase. The primary safety endpoint analysis for the main phase will be performed in the mITT-Wave II analysis set and the primary effectiveness analysis will be performed in the PP-Wave II analysis set.

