5 ANALYSIS SETS

5.1 Main Phase

For the analysis of study endpoints, the analysis sets defined in the following will be used:

- **Full Analysis Set (FAS):** The FAS will consist of all enrolled subjects who have had insertion of the study catheter (with or without delivery of pulse field ablation [PFA]).
- **Modified Intent-To-Treat (mITT) Analysis Set:** The mITT analysis set will consist of enrolled subjects who have had insertion of the study catheter and meet eligibility criteria.

- **Per Protocol (PP) Analysis Set:** The PP analysis set will consist of all enrolled subjects who satisfy the following criteria:
 - Have undergone ablation with the IRE ablation system.
 - Are treated for the study-related arrhythmia.
 - Are without major protocol deviations that would affect the scientific integrity of the primary safety and effectiveness data, including but not limited to the following:
 - Subjects found not meeting eligibility criteria
 - Use of the IRE ablation modality to ablate outside the PV region
 - Failure to check for entrance block for each targeted PV after adenosine/isoproterenol challenge

Eligible subjects treated with commercially available catheters for non-PV triggers that may arise during the index procedure or during repeat procedures occurring during the blanking period will be followed for the full duration of follow-up and will be evaluable for all endpoints in order to preclude potential bias that would arise from exclusion of these subject profiles from endpoint estimates.

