7.4.2 Primary Effectiveness Endpoint

The primary effectiveness endpoint is defined as freedom from documented (symptomatic and asymptomatic) atrial arrhythmia (atrial fibrillation [AF], atrial tachycardia [AT] or atrial flutter

[AFL]) recurrence based on electrocardiographic data (≥ 30 seconds on arrhythmia monitoring device) during the effectiveness evaluation period (Day 91-Day 365). Acute procedural failure (i.e., failure to confirm entrance block in all PVs except those that are silent and/or cannot be cannulated post-procedure, use of a non-study catheter for PV isolation, or failure to have PFA delivery with the study catheter due to IRE system malfunctions) will also be considered a long-term effectiveness failure. Subjects without effectiveness failure who undergo a repeat ablation procedure during the blanking period where PVs were ablated with a commercially available catheter and generator will be considered non-assessable for long-term effectiveness of the IRE ablation system and thus will be excluded from this analysis. The primary analysis of the primary effectiveness endpoint will be performed in the PP analysis set.

The primary effectiveness endpoint will be assessed by testing the following hypothesis:

$$H_0: p_E \leq 0.50 \quad vs \quad H_A: p_E > 0.50 ,$$

Where p_E is the effectiveness success rate.

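### A subject whose vein isolation is completed with a non-study catheter is dropped from the tested effectiveness rate under the protocol but counted as a failure under the Wave II SAP

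*Protocol*

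**What the plan says.** **Protocol, endpoint.** In 8.2.1 (and the synopsis) the acute component of the long-term endpoint is "failure to confirm entrance block, with or without touch-up, in all PVs", apart from silent veins and those that cannot be cannulated. Section 8.2.3 shows what touch-up means: "Ablation by a non-study catheter for PVI (touch-up) among all clinically relevant targeted PVs and by subject". Section 14.2.2.2 foresees the case, since it allows a switch to a commercial RF set-up once the investigator judges that IRE cannot isolate the vein.

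**Protocol, tested set.** Section 20.4.4 states that "the primary effectiveness analysis will be performed in the PP-Wave II analysis set", and 20.4.4.3 repeats this for the final analysis. Section 20.3.2 admits to that set only a subject who "did not require the use of a non-study catheter for Pulmonary Vein Isolation (PVI").

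**Wave II SAP, endpoint.** Section 7.4.2 adds to acute procedural failure "use of a non-study catheter for PV isolation, or failure to have PFA delivery with the study catheter due to IRE system malfunctions", and makes any acute procedural failure a long-term effectiveness failure. The Wave I SAP has the same rule.

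**Wave II SAP, tested set.** "The primary analysis of the primary effectiveness endpoint will be performed in the PP analysis set". Section 5.1 requires that subjects "Have undergone ablation with the IRE ablation system", were treated for the study arrhythmia and had no major deviation. It does not list non-study-catheter use for PV isolation as a reason for exclusion.

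**The concern.** This is a single-arm trial tested against a 50% performance goal, so the result rests on who is in the denominator and who is an event. For one foreseeable kind of subject the two governing documents give different answers to both questions. Two analysts, each following one document, would report different tested rates from the same data.

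Power is also affected. Both documents plan on a 65% success rate and claim over 80% power. The SAP's simulation generates failures only from a post-blanking piecewise-exponential curve, with no separate acute component. A reader cannot tell whether the 65% already allows for subjects who fail because a non-study catheter was used.

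**Working it through.** **1. The same subject under each document.** Take a subject with PFA delivered, one vein completed with a commercial catheter, block confirmed, and no recurrence from Day 91 to Day 365.

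| | Protocol | Wave II SAP |
|---|---|---|
| Acute failure in the primary endpoint? | No (8.2.1) | Yes (7.4.2) |
| In the tested PP set? | No (20.3.2) | Yes (5.1) |
| Contribution to the tested rate | None | One failure |

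The SAP's list of major deviations is open-ended, but the switch to RF is permitted by the protocol and so is not a deviation.

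**2. Effect on the tested rate.** Let t be the share of subjects needing a non-study catheter for isolation. No value is given, so t is an assumption. Assume also that freedom from recurrence is 65% with or without touch-up.

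- Protocol (subjects removed): 0.65(1 − t)/(1 − t) = 65%.
- SAP (subjects kept as failures): 0.65(1 − t).
- Gap: 0.65t, which is 1.3 points at t = 2%, 3.25 at 5% and 5.0 at 7.7%.

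**3. The plan's own power figure.** SAP Table 3.a (realistic enrolment, true safety rate 7%) gives effectiveness power 0.9457 and overall power 0.8395 at 65%. A simulation of the Appendix I design gave 0.973 on a literal reading. It gave 0.946 when dropouts were counted as non-events in the predictive step, and 0.957 when the Gamma(0.1, 0.1) prior was also used at the early look. The 65% row is thus reproduced within about one point under those two variants. The 60% row (0.64 against 0.7289), the early-success share and the stated 1.68% type I error were not reproduced. The figures below therefore rest on the SAP's own table.

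**4. Power if the 65% leaves out touch-up failures.** Linear interpolation in Table 3.a, which gives effectiveness / overall power of 0.9457 / 0.8395 at 65%, 0.8527 / 0.7764 at 62% and 0.7289 / 0.6749 at 60%:

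- t = 2%, rate 63.7%: weight (0.65 − 0.637)/0.03 = 0.433. Effectiveness 0.9457 − 0.433 × 0.0930 = 0.905; overall 0.8395 − 0.433 × 0.0631 = 0.812.
- t = 5%, rate 61.75%: weight (0.62 − 0.6175)/0.02 = 0.125. Effectiveness 0.8527 − 0.125 × 0.1238 = 0.837; overall 0.7764 − 0.125 × 0.1015 = 0.764.
- t = 7.7%, rate 60%: 0.729 and 0.675, read directly from the table.
- Overall power reaches 0.80 at a rate of 0.65 − 0.03 × (0.0395/0.0631) = 0.6312, that is t = 0.0188/0.65 = 2.9%.

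The variant that gave 0.957 in step 3 shows the same pattern. With SAP scoring, effectiveness power is 0.93, 0.85 and 0.61 at t = 2%, 5% and 8%. With touch-up subjects removed, as in the protocol, it is 0.95 at t = 5%.

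**5. Exact fixed-N check.** With a Beta(1,1) prior and Pr(p > 0.5) > 0.9775, the smallest passing counts are 104/180 and 89/153 (180 less 15% dropout). Binomial power at 65%, 63.7% and 61.75% is 0.982, 0.957 and 0.879 for n = 180, and 0.967, 0.933 and 0.840 for n = 153.

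**The case against.** A reader of 8.2.1 alone might infer that the protocol counts a touched-up, arrhythmia-free subject as a success in the test. It does not, because 20.3.2 keeps that subject out of the tested set. The wording of 8.2.1 could produce a pass only where such subjects are retained, for example in the protocol's descriptive mITT summary after early success (20.4.4.3), and nothing is tested there. The mITT sensitivity analyses are defined in the SAP and use the SAP endpoint.

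A reader might also infer that the stated power is wrong. That is not shown. SAP 10.1 calls the rate the proportion free from effectiveness events, and the hazards in 10.6.1 are calibrated to that total. The 65% may therefore already include touch-up failures, with the exponential curve only setting their timing. Nor can a breach of 80% be read off a fixed N of 180. At t = 10% (rate 58.5%) exact power is 0.609 at 180, but 0.765 at 255 and 0.857 at 330 with complete data, and the design can enrol to 330. Table 3.a already shows power down to a 60% rate.

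Finally, 8.2.2 says "Use of a non-study catheter to achieve PVI is considered an acute procedural success failure", which looks like a contradiction of 8.2.1 inside the protocol. It belongs to a separate secondary endpoint, and two endpoints may score touch-up differently. The SAP rule also looks deliberate, as the Wave I SAP's change history records a clarification on this point.

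All of this limits the claim. None of it removes the mismatch between exclusion and failure in the tested rate.

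**Conclusion.** The concern stands in limited form. The protocol (8.2.1 with 20.3.2) and the Wave II SAP (7.4.2 with 5.1) handle non-study-catheter completion of PV isolation differently in the tested primary analysis: excluded in one, failed in the other. The gap in the tested rate is 0.65t, given an assumed touch-up share t and recurrence-freedom that does not depend on touch-up.

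The power consequence is conditional. If the 65% leaves out touch-up failures, effectiveness power is about 0.91, 0.84 and 0.73, and overall power about 0.81, 0.76 and 0.67, at t = 2%, 5% and 7.7%. If the 65% includes them, the stated power is unaffected. The documents do not settle which. Because the SAP scoring can only lower the observed rate relative to exclusion, it does not inflate type I error against the 50% goal. The point should be corrected, but it does not undermine the design.

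**What to change.** Adopt one rule everywhere. The SAP rule is the natural choice, being the stricter one and consistent with protocol 8.2.2.

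- **Protocol 8.2.1 and synopsis:** delete the touch-up phrase and state that use of a non-study catheter for PVI is an acute procedural failure, as in SAP 7.4.2.
- **Protocol 20.3.2:** remove the non-study-catheter exclusion from PP-Wave II so that it matches SAP 5.1 on this point. Amending 8.2.1 alone would leave the tested rates different.
- **SAP 10.2:** state whether the 65% includes touch-up failures. If it does not, restate power at 65% × (1 − t) for a range of t under the adaptive design.
- **SAP 7.4.2:** add one sensitivity analysis that scores touch-up subjects by recurrence only.

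The cost is wording changes in two documents, one extra table and possibly a slightly less favourable power statement.
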